12.1.5 Primary Efficacy Analysis

The primary efficacy variable, (A-a)DO₂, will be tested using an ANCOVA model. This model will have change from baseline to Week 24 in (A-a)DO₂ as the response variable, whilst treatment group, WLL within 2 months prior to randomisation, and baseline (A-a)DO₂ will be predictor variables. The mean difference between each active dose and placebo in change from baseline of (A-a)DO₂ will be estimated, along with its 95% confidence interval (CI) and associated statistical significance test.

Subjects who withdraw from their randomised treatment before week 24 should still be followed up through to week 24. For such patients, their week 24 data will be considered as primary, irrespective of treatment discontinuation, treatment interruption(s), use of rescue

medication (WLL or other), etc. The feasibility and likely meaningfulness of this analysis will be reviewed in the blind review of the SAP, once the extent and pattern of missing data are known.

A sensitivity analysis will include a mixed model for repeated measures including factors for treatment, visit, treatment-by-visit interaction, and baseline (A-a)DO₂.

Subjects who withdraw from the study early and who do not have week 24 data available will have their (A-a)DO₂ measurement imputed using multiple imputation for which full details will be given in the Statistical Analysis Plan. Further sensitivity analyses will include:

- “reasonably worst case” scenario. For the primary analysis, patients in either of the active arms will have the value of the 10th percentile from their dose arm imputed (i.e. approximately the 3rd worst case) whilst patients in the placebo arm will have the median for the placebo arm imputed.
- Tipping point analysis: Patients in any group with a missing endpoint will be assigned progressively worse (A-a)DO₂ to find the point at which the results reverse from favouring the active treatment to the placebo.

All attempts will be made to retain subjects in the trial, even if they wish to withdraw from trial treatment. Hence it is anticipated that there will be only minimal missing (A-a)DO₂ data at week 24 and a further sensitivity analysis will use all available Week 24 data with no imputation (i.e. a “completers” analysis).

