2.2 Secondary Efficacy Endpoints

Key Secondary Endpoints:

- Change from baseline in 6-minute walking distance (6MWD) after 24-weeks treatment
- Change from baseline in SGRQ total score after 24-weeks treatment
- Time to WLL during 24-weeks treatment
- Number of AEs, SAEs, ADRs, severe AEs and AEs leading to treatment discontinuation, including clinically significant changes in laboratory tests and

echocardiographic (ECG) variables, during 24-weeks treatment (hereafter described under Safety Endpoints)

Further Secondary Endpoints:

- Number of WLL over time during 24-weeks treatment (Added in SAP).
- Absolute change from baseline in VC (% predicted), DLCO (% predicted), FEV₁ (% predicted), FVC (% predicted) and relative change from baseline in PaO₂ after 24-weeks treatment
- Number of subjects with >5 mmHg/>0.67 kPa and number of subjects with >10 mmHg/>1.33 kPa improvement in (A-a)DO₂ after 24-weeks treatment
- Number of subjects with >5 percentage points and number of subjects with >10 percentage points improvement in VC (% predicted) after 24-weeks treatment
- Number of subjects with >10 percentage points improvement in DLCO (% predicted) after 24 weeks treatment
- Number of subjects with >10 percentage points improvement in FEV₁(% predicted) after 24-weeks treatment
- Number of subjects with >10 percentage points improvement in FVC (% predicted) after 24-weeks treatment
- Number of subjects with >10% relative improvement in PaO₂ after 24-weeks treatment
- Number of subjects with improved tolerance to exercise (increase in distance walked ≥50 m or desaturation <4 percentage points on the 6MWT) after 24-weeks treatment
- Change from baseline in dyspnoea score and cough scores after 24-weeks treatment
- Number of subjects with improved CT score after 24-weeks treatment

Exploratory Endpoints

Double-blind treatment period

- Absolute change from baseline of (A-a)DO₂, VC (% predicted), DLCO (% predicted), FEV₁(% predicted), FVC (% predicted), and relative change from baseline in PaO₂ after 4 and 12-weeks treatment
- Time period during which the (A-a)DO₂ level is maintained below Baseline minus 10mmHg
- Number of subjects with improved tolerance to exercise (increase in distance walked ≥50 m or desaturation <4 percentage points on the 6MWT) after 4 and 12-weeks treatment
- Time period during which the improvement in tolerance to exercise is maintained
- Change from baseline in dyspnoea score and cough scores after 4 and 12-weeks treatment

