3.2 Determination of Sample Size

The trial is a randomised 3-arm trial in which two thirds of the subjects receive active drug and one third receive placebo.

The sample size calculation was based on data in an earlier trial, where the mean (and standard deviation) (A-a)DO₂ were 31.3 (7.4) before treatment and 12.9 (7.6) after treatment

(all measured in mmHg). The minimum clinically relevant difference to detect between active and placebo arms is considered to be 10-12 mmHg. In order to ensure such an effect size can be detected, a delta of 10 mmHg has been used in the sample size calculation which is based on an unpaired *t*-test of mean difference between the two active arms (combined) vs. placebo, using a significance level of 0.01 and a power of 90%.

The trial will test the null hypothesis

$$H_0: \mu_{\text{diff}} = 0$$

Versus the alternative hypothesis

$$H_1: \mu_{\text{diff}} \neq 0.$$

The calculation was based on an unpaired *t*-test using nQuery Advisor® 7.0. In versions of the protocol including Version 4 and earlier, it was intended that an analysis of the two active dose groups combined, versus placebo, would be carried out, hence the sample size calculation was made based on a 2:1 allocation.

Table 1 Two Group T-Test of Equal Means (Unequal n's)

Test significance level, α	0.010
1 or 2-sided test?	2
Difference in means, $\mu_1 - \mu_2$	10.000
Common standard deviation, σ	7.500
Effect size, $\delta = \mu_1 - \mu_2 / \sigma$	1.333
Power (%)	90
n_1	14
n_2	28
Ratio: n_2 / n_1	2.000
$N = n_1 + n_2$	42

Based on the assumption listed in Table 1, above, 42 subjects would initially be required to be randomised.

Based on a subsequent evaluation of variability and plausible effect sizes for the key secondary endpoints, the sample size was increased to 90 subjects (30 subjects in each treatment arm) in Substantial Protocol Amendment 11 (06 June 2017), to increase the power to identify statistically significant treatment effects also on one or more of the key secondary endpoints.

Very limited data on these secondary endpoints are available but with a sample size of 30 subjects per group, it would be possible to show a treatment effect of 50 m on the 6MWD (assuming a SD of 50) or of 10 points on the SGRQ (assuming a SD of 10) with approximately 90% power.

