From these sample size calculations conducted in January 2018 it was clear that the two key secondary endpoints with highest power to detect a clinically relevant difference between treatment groups based on the least number of subjects were SGRQ Total Score and 6MWD. Based on the pre-defined criterion that the sample size would be increased to attain 90% power for at least 2 of the 3 key secondary endpoints, the results indicate that the critical endpoint is the 6MWD, which would require that the sample size should be increased to at least $43 \times 3 = 129$ randomised subjects. After reviewing the results from the sample-size recalculation it was decided by Savara ApS to increase the sample size to $45 \times 3 = 135$ randomised subjects. Any subjects already in screening at the time of reaching 135 randomised subjects would also be randomised, if otherwise eligible for the trial.

The detailed results of the sample size re-estimation were documented in a separate report and are available in Appendix 2 to the SAP.

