All assessed (A-a)DO₂ measurements, and the corresponding changes from baseline will be summarised by visit and treatment group. In addition, similar summaries of (A-a)DO₂ will also be produced excluding data collected during treatment discontinuation, treatment interruption(s) and use of rescue medication (WLL or other). The decision of what data will be excluded and the reason will be identified during the blind review of data and documented in the "Pre-analysis-review"-document before data base lock (DBL).

Mean profiles for (A-a)DO₂ observed values and change from baseline over time will be provided.

Sensitivity Analyses

The following sensitivity analyses for the primary endpoint will be done in order to evaluate the robustness of the results in relation to influence of any missing data. The sensitivity analyses should be considered supportive analyses and will thus not be part of the procedures applied to control type-1 error rate for testing hypotheses for primary and key secondary efficacy endpoints as described in section 5.4.

- A mixed model for repeated measures (MMRM) will be applied including fixed, categorical effects for treatment, WLL (stratification), visit, treatment-by-visit interaction, Japan vs other countries, and fixed covariates for baseline (A-a)DO₂. An unstructured covariance matrix will be applied to model the within-subject errors, if possible. If this analysis fails to converge, compound symmetry will be tested. Kenward-Roger approximation will be used to estimate denominator degrees of freedom. This methodology does not require imputation of missing data. Instead missing data is modelled based on the subjects' available data and on other subjects' data over time (this approach is valid under assumption that data is missing according to 'Missing at Random' (MAR)) [2].

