- Subjects who withdraw from the study early and who do not have week 24 data available will have their (A-a)DO₂ measurement imputed using multiple imputation (MI). This will be done by first ensuring a monotone missing data pattern by imputation of intermediate missing data (baseline, Week 4 and Week 12) by a Markov chain Monte Carlo (MCMC) approach, where imputations are done by treatment group Japan vs other countries, and WLL (stratification) if possible (strata may be dropped depending on the number of observations per combination). The imputation will be done generating 10 data sets. When monotone missingness has been accomplished, then the remaining missing data, up to and including Week 24, will be imputed using a monotone regression approach using treatment and WLL (stratification) as class variables. Each replication of the data, including the imputed missing values, will then be analysed using the ANCOVA used in the primary analysis, and estimates will be pooled using proc MIANALYZE SAS®. (this approach is valid under assumption that data is missing according to MAR).

- If superiority has been determined for any of the comparisons planned for the primary endpoint, a tipping point analysis (TP) will be applied where subjects with a missing endpoint (Week 24) in the group for which superiority has been determined will be assigned progressively worse (A-a)DO₂. This will be done by generating imputed data according to the previous step and using the MNAR option in proc MI SAS® to adjust imputed Week 24 data with an appropriate sized shift parameter in the superior arm in an iterative manner until the results shift from significant (P<0.05) to non-significant (P>0.05). From this analysis, results will be presented including overall estimates at the tipping point, as well as descriptive statistics for imputed data vs non-imputed data.
- A “reasonably worst case” scenario. For the primary analysis, patients in either of the active arms will have the value of the 10th percentile from their dose arm imputed (i.e. approximately the 3rd worst case) whilst patients in the placebo arm will have the median for the placebo arm imputed. This analysis will be based on the same ANCOVA model as applied for the primary analysis.

The above sensitivity analyses can be considered as de-facto approaches. The following sensitivity analyses will also be conducted as de-jure estimation approaches to evaluating data:

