14.2 EFFICACY DATA									
Primary Endpoint									
Table	14.2.1.1	Summary of (A-a)DO2 and change from baseline in (A-a)DO2 by visit during 24 weeks treatment		X	X				
Figure	14.2.1.2	Mean profiles of (A-a)DO2 over time		X					
Figure	14.2.1.3	Mean change profiles of (A-a)DO2 over time		X					
Table	14.2.1.4	Summary of (A-a)DO2 and change from baseline in (A-a)DO2 while on treatment by visit during 24 weeks treatment		X					
Table	14.2.1.5	Analysis of primary endpoint change from baseline in (A-a)DO2 after 24 weeks (ANCOVA)		X					
Table	14.2.1.6	Sensitivity analysis for primary endpoint change from baseline in (A-a)DO2 after 24 weeks (MMRM)		X					
Table	14.2.1.7	Sensitivity analysis for primary endpoint change from baseline in (A-a)DO2 after 24 weeks (ANCOVA) multiple imputation analysis		X					
Table	14.2.1.8	Sensitivity analysis for primary endpoint change from baseline in (A-a)DO2 after 24 weeks (ANCOVA) multiple imputation of measurements following WLL		X					
Table	14.2.1.9	Sensitivity analysis for primary endpoint change from baseline in (A-a)DO2 after 24 weeks (ANCOVA) tipping point analysis		X					
Table	14.2.1.10	Sensitivity analysis for primary endpoint change from baseline in (A-a)DO2 after 24 weeks (ANCOVA) worst case analysis		X					
Table	14.2.1.11	Sensitivity analysis for primary endpoint change from baseline in (A-a)DO2 after 24 weeks (ANCOVA) completer analysis		X					
Table	14.2.1.12	Sensitivity analysis for primary endpoint change from baseline in (A-a)DO2 after 24 weeks (ANCOVA)			X				
Table	14.2.1.13	Summary of (A-a)DO2 and change from baseline in (A-a)DO2 by visit during 24 weeks treatment by Age Group		X					
Table	14.2.1.14	Summary of (A-a)DO2 and change from baseline in (A-a)DO2 by visit during 24 weeks treatment by Sex		X					
Table	14.2.1.15	Summary of (A-a)DO2 and change from baseline in (A-a)DO2 by visit during 24 weeks treatment by aPAP severity		X					
Table	14.2.1.16	Summary of (A-a)DO2 and change from baseline in (A-a)DO2 by visit during 24 weeks treatment by aPAP diagnosis		X					
Table	14.2.1.17	Summary of (A-a)DO2 and change from baseline in (A-a)DO2 by visit during 24 weeks treatment – by strata		X					
Figure	14.2.1.18	Mean profiles of (A-a)DO2 over time by region		X					
Table	14.2.1.19	Summary of (A-a)DO2 and change from baseline in (A-a)DO2 by visit during 24 weeks treatment – by region		X					
Figure	14.2.1.20	Mean profiles of (A-a)DO2 over time by strata		X					

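### The reasonably-worst-case imputation names the 10th percentile for active patients, which is a near-best value because lower (A-a)DO₂ is better

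*SAP*

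**What the plan says.** SAP 5.3.6 lists a reasonably-worst-case scenario among the sensitivity analyses of the primary endpoint. Patients in either active arm "will have the value of the 10th percentile from their dose arm imputed (i.e. approximately the 3rd worst case"; patients on placebo receive the median of the placebo arm. The completed data then go into the primary ANCOVA. Protocol 12.1.5 has the same wording. SAP Appendix 1 gives the output as Table 14.2.1.10, "Sensitivity analysis for primary endpoint change from baseline in (A-a)DO2 after 24 weeks (ANCOVA) worst case analysis".

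Both documents treat a fall in (A-a)DO₂ as benefit. An exploratory endpoint in SAP 2.2 measures how long the "level is maintained below Baseline minus 10mmHg", and the trial used for sizing went from "31.3 (7.4) before treatment and 12.9 (7.6) after treatment" (SAP 3.2, mmHg).

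On the status of the analysis, SAP 5.3.6 states: "The sensitivity analyses should be considered supportive analyses". On missing data, protocol 12.1.5 says that "it is anticipated that there will be only minimal missing" Week 24 data.

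**The concern.** The operative statistic and its explanation point to opposite tails. Where low is good, the numerical 10th percentile of an arm is near its best result, whether it is taken on the Week 24 value or on the change from baseline (the most negative change is best). Neither document ranks percentiles from the worst end or reverses the sign of the change. A programmer who codes the percentile as written gives active patients with missing data a near-best outcome and placebo patients a middling one, and the result is reported as a worst case.

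This analysis has a particular job. The MMRM and multiple-imputation analyses assume data missing at random, and the re-imputation after rescue reuses the same imputation method. The completer and per-protocol analyses impute nothing. The tipping-point analysis is correctly oriented, but the SAP makes it conditional: "If superiority has been determined for any of the comparisons planned for the primary endpoint, a tipping point analysis (TP) will be applied". Protocol 12.1.5 sets no such condition. The worst-case scenario is therefore the only departure from missing-at-random imputation of the primary endpoint that the SAP runs whatever the result.

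There are two smaller gaps in the same sentence. It does not say whether the imputed value is the Week 24 value or the change. Its rank of third also fits the former arm size, not the present one.

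**Working it through.** **Inputs from the documents.** Common SD 7.5 mmHg and design difference 10 mmHg (protocol 12.2, Table 3; SAP 3.2, Table 1). Post-treatment mean 12.9, SD 7.6 (same sections). Arm size 30 in protocol 12.2; for the current size, SAP 3.2 says "it was decided by Savara ApS to increase the sample size to" 45 × 3 = 135.

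**Assumptions.** Missing rates of 2%, 5%, 10% and 15% per arm (the plan gives none); missing completely at random; correlation of 0.5 between baseline and Week 24. With SD 7.5 at both times, this makes the SD of change √(2 × (1 − 0.5)) × 7.5 = 7.5.

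**Step 1: the plan's rank.** 0.10 × 30 = 3, so the number three reproduces at 30 per arm. The direction does not. In ascending order of 30, the SAS default 10th percentile has rank 3.5 from the lowest (best), which is 30 + 1 − 3.5 = 27.5 from the worst. At 45 per arm, 0.10 × 45 = 4.5; the SAS rank is 5th from the best, or 45 + 1 − 5 = 41st worst.

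**Step 2: size of the imputed value.** The offset from the arm mean is z × SD, with z(0.10) = −1.2816 and z(0.90) = +1.2816.
- SD 7.5: 1.2816 × 7.5 = 9.61 mmHg better (10th percentile) or worse (90th), a gap of 19.2 mmHg. For SD 5 to 10 the gap is 12.8 to 25.6 mmHg.
- On the post-treatment level of the sizing trial: 12.9 − 1.2816 × 7.6 = 3.2 mmHg (10th), against 12.9 + 1.2816 × 7.6 = 22.6 mmHg (90th).

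**Step 3: shift in the treatment comparison.** The placebo median leaves the placebo mean unchanged in expectation, so the shift is the missing rate × 9.61. The literal rule moves it towards active; the upper tail moves it by the same amount against.

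**Step 4: simulation.** Three arms of 45, 4,000 runs per cell, one ANCOVA on change with treatment and baseline (without the WLL and Japan terms), once daily against placebo. Entries are the percentage of trials in which active is significantly better at the two-sided 5% level. Ranges in the no-effect columns cover percentiles taken on the change and on the Week 24 value; the 5 mmHg columns use the change.

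| Missing per arm (assumed) | Shift, mmHg (step 3) | No effect, literal | No effect, upper tail | Effect 5 mmHg, literal | Effect 5 mmHg, upper tail |
|---|---|---|---|---|---|
| 2% | 0.19 | 3.4 | 1.8–2.0 | 96 | 93 |
| 5% | 0.48 | 5.3–5.6 | 1.2–1.5 | 97 | 89 |
| 10% | 0.96 | 10.7–11.1 | 0.6–0.9 | 98 | 79 |
| 15% | 1.44 | 18.6–19.3 | 0.4 | 99 | 70 |

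The nominal rate in the no-effect columns is 2.5%. At a true effect of 5 mmHg, the mean estimates were −5.19, −5.44, −5.89 and −6.36 (literal) and −4.83, −4.52, −4.06 and −3.61 (upper tail), in line with step 3. At the 10 mmHg design effect they were −10.2 to −11.4 and −9.8 to −8.7, and about 100% of trials were significant under both readings.

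The simulation standard error is √(0.034 × 0.966 / 4000) = 0.3 percentage points at the low end of the literal column and √(0.19 × 0.81 / 4000) = 0.6 at the high end.

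**Step 5: sensitivity to the correlation.** With correlation 0.3 to 0.7, the last column becomes 85–99%, 81–98%, 69–95% and roughly 55–90%. The direction of the difference between readings does not change.

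**The case against.** The strongest reply is that this is a slip of wording. The name of the scenario, the gloss after the percentile and the table title all say worst, so a programmer would have to ignore three cues, and nobody would have to notice a worst-case estimate better than the completer estimate beside it. That makes the intent clear, but the percentile remains the instruction that gets coded. The gloss is also a weak corrective, because its rank is out of date.

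Secondly, the tipping-point analysis runs whenever a primary comparison is positive, which is when a stress test against the drug is most needed. This stands, and it limits the harm.

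Thirdly, no-effect rates treat a supportive analysis as a test in its own right. Most of the literal-rule positives arise in trials whose observed-data ANCOVA is not significant: 3.8 of 6.3, 7.2 of 9.9 and 17.3 of 19.9 percentage points at 5%, 10% and 15% missing. Such trials support no primary claim. But where the observed-data ANCOVA was falsely significant, the upper-tail rule lost significance in about 21% to 86% of trials at 2% to 15% missing, and the literal rule almost never did.

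Fourthly, the large effects need more missing data than the protocol expects. At 2% to 5% the shift is only 0.2 to 0.5 mmHg, against a design difference of 10. This stands. So does the point that the rank and the scale matter little numerically: the rank is labelled approximate, and the two scales give nearly the same results.

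**Conclusion.** The concern holds. As written, the rule imputes a near-best value for active patients in an analysis meant to penalise them; this is a wrong instruction, not a missing detail. It misplaces the imputed value by about 19 mmHg at the plan's SD. The effect on the comparison is proportional to the missing rate: negligible at 2%, and about 1 mmHg in the wrong direction at 10%. The significance rates rest on assumed missing rates, data missing completely at random, normal data with SD 7.5 and, for the 5 mmHg results, the assumed correlation and a chosen effect of half the design difference. The direction of the error rests only on lower being better. The primary test and type I error control are untouched, and at the design effect the conclusion is the same under either reading. It should be corrected, but it does not threaten the trial's main claim.

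**What to change.** Before unblinding, replace the sentence in SAP 5.3.6 with a rule to this effect: *active-arm patients with a missing Week 24 endpoint receive the numerical 90th percentile (higher is worse) of the observed subjects in their own arm; placebo patients receive the placebo median on the same scale.* The sponsor should state whether that scale is the Week 24 value or the change from baseline. The rank should be deleted, or updated to about the fourth to fifth worst of 45. Because protocol 12.1.5 has the same wording, the correction should be listed among the changes in SAP 5.1. If the SAP is not to be reissued, the pre-analysis review document described in SAP 5.2, signed before unblinding, could carry the clarification.

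The cost is one sentence, one line in the list of changes and one programming parameter, with no new data. The sensitivity result will be less favourable to the drug than under the literal rule. Reversing the tail after unblinding would be much harder to defend.
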